5.1 Study Treatments and Formulations

[REDACTED]

5.2 Control Treatments

For cohort 1 in stage 1, the control treatment will be a sham procedure. For cohorts 2 through 6D in stage 1, patients will receive [REDACTED] vehicle [REDACTED]

[REDACTED] in the contralateral eye. [REDACTED]

[REDACTED] For stage 2, patients in treatment group 1 will receive [REDACTED] vehicle in both eyes.

[figure not shown]
5.3 Methods for Masking

This study requires a treating investigator and a follow-up investigator. Certain study tests and procedures are assigned to the treating investigator to maintain masking of the follow-up investigator to the study treatments. The treating investigator will conduct RESTASIS X [REDACTED] administration, macroscopic regional hyperemia, slit lamp biomicroscopy (eyelids, margins, lashes, and conjunctiva), impression cytology for biomarker analysis, and all dilated ophthalmic examinations. The follow-up investigator or appropriately qualified site personnel will administer all other procedures. See Table 5 for a listing of investigator's procedure assignments. The site personnel conducting photographic conjunctival hyperemia assessments may assist with study tasks consistent with the role of the treating investigator. In addition, RESTASIS X kit components will be labeled in a manner that maintains preparation and administration in a masked fashion. In stage 1, follow-up investigators and patients will be masked with regard to the identity [REDACTED]. In stage 2, follow-up investigators and patients will be masked with regard to the identity and dose [REDACTED]. For further description of the kits, see Section 9.5.2.

5.4 Treatment Allocation Ratio and Stratification

Stage 1: Within each cohort, each patient will be randomly assigned with respect to the eye, right or left, to receive F1 or F2 (vehicle for cohort 1). The contralateral eye will receive vehicle (sham for cohort 1) (see Table 1).

Stage 2: Patients will be allocated in a randomized fashion to the treatment groups shown in Table 2. This randomization will be stratified by Sjögren's syndrome (presence or absence of Sjögren's syndrome) at screening. Patients in treatment group 1 will be assigned to receive vehicle in both eyes as the baseline treatment, and patients in treatment groups 2 and 3 will be assigned to receive CFI [REDACTED], respectively, in both eyes as the baseline treatment. Table 6 shows the randomization/stratification groups.

5.5 Method for Assignment to Treatment Groups/Randomization

Prior to initiation of study treatment, each patient who provides informed consent will be assigned a patient number that will serve as the patient identification number on all study documents.

An automated interactive voice response system (IVRS)/interactive web-based response system (IWRS) will be used to manage the randomization, stratification, and treatment assignment.

Stage 1:

For each cohort, Allergan Biostatistics will prepare a scheme that will randomly assign patients with respect to the eye, right or left, to receive F1 or F2 (vehicle for cohort 1) (see Table 1). At baseline, if the patient is eligible to be randomized, the IVRS/IWRS will assign the next available randomization number for that cohort to the patient at the time the investigator requests randomization.

Stage 2:

Allergan Biostatistics will prepare a scheme that will randomly assign patients to 1 of 3 treatment groups (Table 2). The randomization will be stratified by Sjögren's syndrome (presence or absence of Sjögren's syndrome at screening).

At baseline, if the patient is eligible to be randomized, he/she will be assigned to a treatment group through the IVRS/IWRS. Randomization numbers will be assigned in blocks for each Sjögren's stratum (absent/present). Based on the randomization scheme, a randomization number will be assigned to each patient sequentially according to the order of enrollment in the stratum. That is, IVRS/IWRS will assign the next available randomization number to the patient at the time the investigator requests randomization. The treatment-group assignment will be based on an equal allocation ratio across the study (not by site).

For both stages, study medication labeled with medication kit numbers will be shipped to each study site. The IVRS/IWRS will report a medication kit number to use for each patient corresponding to the randomization number. Sites will receive the IVRS/IWRS confirmation notifications for each transaction. All notifications are to be maintained with the study source documents.

5.6 Treatment Regimen and Dosing

Following a 2-week run-in period whereby signs and symptoms of dry eye disease will be verified and washout of artificial tears other than REFRESH PLUS will be facilitated by run-in with REFRESH PLUS, [REDACTED] RESTASIS X or vehicle will be initiated. [REDACTED]
[REDACTED] Each eye will receive either vehicle or [REDACTED] RESTASIS X.

5.7 Storage of Study Medications/Treatments

The study medication must be stored in a secure area and administered only to patients entered into the clinical study, at no cost to the patient, and in accordance with the conditions specified in this protocol.

[REDACTED]

[REDACTED]

5.8 Preparation of Study Medications/Treatments

A detailed description of the study drug preparation procedure will be provided in the procedure manual. [REDACTED]

[REDACTED]

5.9 Treatment Administration

The study drug administration will be conducted in an office setting or in a surgical suite.

[REDACTED]

[REDACTED]. For stage 1, F1 or F2 will be administered to the study eye per the study protocol. For stage 2, vehicle will be administered to both eyes in treatment group 1, and CFI will be administered to both eyes in treatment groups 2 and 3. A detailed description of the study drug administration procedure will be provided [REDACTED]

[REDACTED]

5.10 Retreatment

In stage 1 of the study, patients in cohorts 6C and 6D will be retreated (at week 12) [REDACTED]

[REDACTED]

[REDACTED]

[REDACTED]

[REDACTED]

To help guide the investigator's decision on retreatment, [REDACTED] unless a $\geq +2$ hyperemia grade [REDACTED] is present, at which time the investigator may elect not to retreat the patient in stage 1. In this case, the

Approval Date: 19-Jan-2017

patient will not be retreated in either eye but continue to be observed for safety (see Table 3) for the duration of the study. [REDACTED]

For stage 2, patients in treatment groups 2 and 3 will be retreated (at week 12) with CFI in both eyes at the same dose used for the baseline (day 1) [REDACTED] Treatment group 1 patients will be retreated at week 12 with vehicle. If retreatment is not administered, the patient will continue to be observed for safety (see Table 4) and exited at the Week 24/Week 12R/Exit visit.

In stage 2, the investigator can elect to [REDACTED] if a $\geq +2$ hyperemia grade [REDACTED] is present. [REDACTED]

[REDACTED]

[REDACTED]

6 Response Measures and Summary of Data Collection Methods

6.1 Safety Measures

For stages 1 and 2, the following safety measures will be examined:

- adverse events (ocular and nonocular)
- BCVA
- macroscopic hyperemia assessment and slit-lamp biomicroscopy
- IOP
- dilated ophthalmic exam
- photographic conjunctival hyperemia assessment

- vital signs
- laboratory tests (chemistry, hematology, urinalysis)
- urine pregnancy test

Laboratory test results will be forwarded from the central laboratory to the study site and to Allergan or its designee. The laboratory results from screening will be reviewed prior to randomization. Laboratory tests at screening may be repeated once at the discretion of the investigator and pending discussion with Allergan, to confirm exclusionary status. Study treatment will be performed only if the investigator deems the laboratory results to be acceptable. The most current specimen results will be reviewed prior to randomization. The investigator will review all laboratory results for the clinical significance of any abnormalities. Evaluation and management of abnormal laboratory results should be conducted according to local site practice. Clinically significant abnormalities are to be recorded on an adverse event electronic case report form (eCRF) page.

6.2 Pharmacokinetic Measures

Stage 1:

Ocular and systemic pharmacokinetic samples will be collected (Table 3). For determinations of drug concentration in the tear film, tear samples will be collected from both eyes at baseline (prior to treatment), weeks 1, 4, 8, 12, and 24/12R or Exit for cohorts 2 through 6D. For determination of drug concentration in the circulation, blood samples will be collected at baseline (prior to treatment), weeks 1, 4, 8, 12, and 24/12R or Exit for cohorts 2 through 6D. For cohorts 6C and 6D only, tear and blood samples will be collected post retreatment at weeks 1R, 4R, and 8R, and 24/12R or Exit (see Table 3).

Stage 2:

Ocular drug concentrations will be determined from tears sampled at baseline (prior to treatment), weeks 1, 4, 8, 12, and post-retreatment at weeks 1R, 4R, 8R, and 24/12 R or Exit (see Table 4). For determination of systemic drug concentration, blood samples will be collected at baseline (prior to treatment), weeks 1, 4, 8, 12, and post retreatment at weeks 1R, 4R, 8R, and 24/12R or Exit (see Table 4).

[REDACTED]

[REDACTED]

6.3.1 Health Outcomes Measures

In stage 1, a Supplemental Dry Eye Patient Reported Outcomes (PRO) Questionnaire, developed to assess symptoms individually in each eye, will be administered at the study visits indicated in Table 3. In stage 2, the Supplemental Dry Eye PRO Questionnaire and the Dry Eye Treatment Satisfaction PRO will be administered at the study visits indicated in Table 4.

[REDACTED]

- [REDACTED]
- [REDACTED]
- [REDACTED]
- [REDACTED]
- [REDACTED]

Approval Date: 19-Jan-2017

An IVRS/IWRS will be used to assign patient identification numbers, patient initials, randomize/stratify patients, and manage study medication inventory. Data will be transferred to Allergan on a periodic basis throughout the study.

Qualified laboratories will be used for the analysis of blood and urine samples. Laboratory data will be transferred to Allergan on a periodic basis throughout the study.

A qualified image reading center will be used to collect and analyze photographs taken by the study sites. Photographs will be transferred from the reading center to Allergan on a periodic basis. All digital images will be transferred from the reading center to Allergan at the end of the study.

In the event external data need to be captured within the eCRFs by the vendor, the vendor will handle the data as a site would and the vendor will be responsible for ensuring that these data are properly recorded on each patient's eCRFs and related documents. A vendor representative will also be required to sign for the eCRFs that they have completed.

7 Statistical Procedures

[REDACTED]

[REDACTED] An interim database lock of stage 1 will not be conducted until after all patients in cohorts 1 through 6B complete the study and all patients in cohorts 6C and 6D completed at least week 1 following retreatment. An interim database lock of stage 2 will not be conducted until after all patients in stage 2 complete at least week 1 following retreatment. A final database lock will occur after all enrolled patients have completed stage 2 of the study. The statistical analysis plan (SAP) will be developed and finalized before database lock.

7.1 Analysis Populations

The safety population will include all treated patients. This population will be used for the safety analyses. The modified intent-to-treat (mITT) population will be all patients who are treated and have baseline and at least 1 postbaseline assessment for 1 or more of the exploratory efficacy measurements (see Section 6.3). The mITT population will be used for the exploratory efficacy analyses. The population consisting of subjects who received the active study treatment will be used for pharmacokinetic analysis.

7.2 Collection and Derivation of Exploratory Efficacy Assessments

Exploratory efficacy (stage 1 and stage 2) measures (Section 6.3) will be evaluated. Baseline and change from baseline measure will be assessed. Also, number (percent) of responders may be assessed.

7.3 Hypothesis and Methods of Analysis

In general, continuous variables will be summarized by descriptive statistics including sample size (N), mean, standard deviation, median, minimum and maximum. Categorical variables will be summarized by frequency count and percentage.

7.3.1 Safety Analyses

Safety measures will be analyzed using the safety population. The Medical Dictionary for Regulatory Activities (MedDRA) nomenclature will be used to code adverse events. The number and percentage of patients with treatment-emergent adverse events will be summarized. The adverse events will be classified into ocular and nonocular types and will be summarized separately. Detailed methods for the analyses of adverse events and other safety variables will be described in the SAP.

[REDACTED]

[REDACTED]

Approval Date: 19-Jan-2017

[Redacted]

7.4 Subgroup Analyses

Subgroup analyses will be conducted for all safety and efficacy measures by presence and absence of Sjögren’s syndrome for stage 2. No other subgroup analyses are planned, but they may be performed for exploratory purposes.

7.5 Sample Size Calculation

The sample sizes for both stages 1 and 2 are determined empirically.

7.6 Interim Analyses

An interim database lock of stage 1 will not be conducted until after all patients in cohorts 1 through 6B complete the study and all patients in cohorts 6C and 6D complete at least week 1 following retreatment. An interim database lock of stage 2 will not be conducted until after all patients in stage 2 completed at least week 1 following retreatment. Statistical analyses will be performed following each database lock to support the design of future clinical studies.

8 Study Visit Schedule and Procedures

[Redacted]

Approval Date: 19-Jan-2017

[Redacted text block]

[Redacted text block]

8.1 Patient Entry Procedures

8.1.1 Overview of Entry Procedures

Prospective patients will be considered for entry into this study by applying the criteria in Sections 4.3 and 4.4 (inclusion/exclusion criteria) at the screening and baseline visits.

8.1.2 Informed Consent and Patient Privacy

The study procedures will be discussed with the patient. Any patient wishing to participate must give informed consent prior to any study-related procedures or change in treatment. The patient must also give authorization and other written documentation in accordance with the relevant local privacy requirements (where applicable) prior to any study-related procedures or change in treatment.

Patients who provide informed consent will be assigned a patient number that will be used on patient documentation throughout the study.

8.2 Washout Intervals/Run-in

For patients not on RESTASIS at the screening visit, there will be a 2-week run-in period with REFRESH PLUS, for use 4 times per day. If patients are using topical RESTASIS at screening, their screening period will be extended to a 13-week period to allow for washout of topical RESTASIS in conjunction with the 2-week run-in with REFRESH PLUS. Any screening diagnostic procedures that were performed at the start of the extended screening period will be repeated within days -14 to -2.

Approval Date: 19-Jan-2017

8.3 Procedures for Final Study Entry

During the 2-week run-in period, signs and symptoms of dry eye disease will be verified in both eyes at screening (week -2) and baseline (day 1) visits. Specific scores for qualification tests can be found in the inclusion criteria (Section 4.3).

Female patients of childbearing potential MUST have a negative urine pregnancy test result at screening (week -2) and baseline (day 1) visits. Only eligible patients will be enrolled into the study. A patient is considered to have enrolled in the study at the time of randomization to treatment at baseline (day 1).

See Section 5.5 for the method of assignment to treatment groups/randomization.

8.4 Visits and Associated Procedures

[REDACTED]

- | [REDACTED]
- | [REDACTED]
- | [REDACTED]
- | [REDACTED]
- | [REDACTED]
- | [REDACTED]
- | [REDACTED]
- | [REDACTED]
- | [REDACTED]
- | [REDACTED]
- | [REDACTED]

Approval Date: 19-Jan-2017

- [REDACTED]

[REDACTED] [REDACTED]

- 1 [REDACTED]

- 1 [REDACTED]

- 1 [REDACTED]

- 1 [REDACTED]

- 1 [REDACTED]

- 1 [REDACTED]

- 1 [REDACTED]

 - [REDACTED]

- 1 [REDACTED]

- 1 [REDACTED]

- 1 [REDACTED]

- 1 [REDACTED]

[REDACTED] [REDACTED]

- 1 [REDACTED]

- 1 [REDACTED]

- 1 [REDACTED]

- 1 [REDACTED]

- 1 [REDACTED]

- 1 [REDACTED]

- 1 [REDACTED]

Approval Date: 19-Jan-2017

[Redacted]

[Redacted]

[Redacted]

[Redacted]

[Redacted]

[Redacted]

[Redacted]

[Redacted]

[Redacted]

[Redacted]

[Redacted]

[Redacted]

[Redacted]

[Redacted]

[Redacted]

[Redacted]

[Redacted]

[Redacted]

[Redacted]

[Redacted]

[Redacted] P

Approval Date: 19-Jan-2017

- | [REDACTED]
- | [REDACTED]
- | [REDACTED]
- | [REDACTED]
- | [REDACTED]
- | [REDACTED]

[REDACTED] [REDACTED]

- | [REDACTED]
- | [REDACTED]
- | [REDACTED]
- | [REDACTED]
- | [REDACTED]
- | [REDACTED]
- | [REDACTED]
- | [REDACTED]
- | [REDACTED]
- | [REDACTED]
- | [REDACTED]
- | [REDACTED]
- | [REDACTED]
- | [REDACTED]
- | [REDACTED]

Approval Date: 19-Jan-2017

[Redacted]

- | [Redacted]
- | [Redacted]
- | [Redacted]
- | [Redacted]
- | [Redacted]
- | [Redacted]
- | [Redacted]
- | [Redacted]
- | [Redacted]

[Redacted]

- | [Redacted]
- | [Redacted]
- | [Redacted]
- | [Redacted]
- | [Redacted]
- | [Redacted]
- | [Redacted]
- | [Redacted]
- | [Redacted]
- | [Redacted]
- | [Redacted]

Approval Date: 19-Jan-2017

[REDACTED]

- | [REDACTED]
- | [REDACTED]
- | [REDACTED]
- | [REDACTED]
- | [REDACTED]
- | [REDACTED]
- | [REDACTED]
- | [REDACTED]
- | [REDACTED]
- | [REDACTED]
- | [REDACTED]
- | [REDACTED]
- | [REDACTED]
- | [REDACTED]
- | [REDACTED]
- | [REDACTED]
- | [REDACTED]
- | [REDACTED]
- | [REDACTED]
- | [REDACTED]
- | [REDACTED]

[REDACTED]

- | [REDACTED]

Approval Date: 19-Jan-2017

- [REDACTED]
- [REDACTED]
- [REDACTED]
- [REDACTED]
- [REDACTED]
- [REDACTED]

8.5 Instructions for the Patients

Patients are to be instructed not to instill REFRESH PLUS within 6 hours prior to a study visit.

Patients will be instructed to strictly follow the study visit schedule and to report all changes in condition to the investigative site.

Instruction should be given to the patient to maintain a stable dose whenever possible of any chronically used concomitant medication. Patients should be instructed to communicate any changes to their medication or any new medications at their next study visit. Patients should also be reminded to contact the study site if they are experiencing any ocular or nonocular medical changes between study visits, or if they have had any medical procedures (including diagnostic procedures) performed between study visits.

8.6 Unscheduled Visits

Unscheduled visits can be performed if safety concerns arise, at the discretion of the investigator. Additional examinations may be performed as necessary to ensure the safety and wellbeing of patients during the study.

If a patient is seen for an unscheduled visit, an assessment and record of adverse events should be completed. Additional evaluations should be performed as necessary, and the appropriate eCRFs should be completed.

8.7 Compliance With Protocol

Patients will be scheduled for follow-up visits and these should occur as closely as possible to the day specified in the visit schedule.

Approval Date: 19-Jan-2017

At each postbaseline visit, the investigator or designee will ask patients if they have been compliant with use of only REFRESH PLUS (up to 4 times per day, both eyes), used any concomitant medications, or have had any medical procedure performed since the previous visit.

8.8 Early Discontinuation of Patients

Patients may voluntarily withdraw from the study at any time; these patients will be encouraged to return for the week 24/12R or Exit visit and have exit procedures completed when possible.

Notification of early patient discontinuation from the study and the reason for discontinuation will be made to Allergan and will be clearly documented on the appropriate eCRF.

8.9 Withdrawal Criteria

The investigator and Allergan have the right to withdraw a patient from the study at any time for any reason. When possible, the decision to withdraw a patient from study treatment or the study should be discussed with Allergan.

Patients should be discontinued from the study if any of the following criteria are met:

- patient develops (or has an exacerbation of) any medical condition that, in the opinion of the investigator, would put the patient at an unacceptable medical risk or compromises the patient's ability to participate in the study
- patient is unwilling or unable to continue to comply with study procedures

Patients who are withdrawn early from the study during a study visit should have the exit procedures completed when possible.

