Natural menopause is defined as the permanent cessation of menstrual periods, determined retrospectively after a woman has experienced 12 months of amenorrhea without any other obvious pathological or physiological cause. For women of childbearing potential who may participate in the study, the following methods of contraception, if properly used, are generally considered reliable: oral contraceptives, patch contraceptives, injection contraceptives, male condom with intravaginal spermicide, diaphragm or cervical cap with spermicide, vaginal contraceptive ring, intrauterine device, surgical sterilization (bilateral tubal ligation), vasectomized partner, or sexual abstinence.

The investigator and each patient will determine the appropriate method of contraception for the patient during their participation in the study.

If a female becomes pregnant during the study, the investigator will notify Allergan immediately after the pregnancy is confirmed and the patient will be exited from the study after appropriate safety follow-up. The investigator will (1) notify the patient's physician that the patient was being treated with an investigational drug (RESTASIS X/CsA), and (2) follow the progress of the pregnancy. The investigator must document the outcome of the pregnancy and provide a copy of the documentation to Allergan.

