4.5.2 Prohibited Medications/Treatments

The decision to administer a prohibited medication/treatment is done with the safety of the study participant as the primary consideration. When possible, Allergan should be notified before the prohibited medication/treatment is administered.

The following medications or classes of medications are prohibited during the study:

- any systemic/dermatological/ophthalmic use of RESTASIS/CsA or other calcineurin inhibitors
- any artificial tear product other than REFRESH PLUS
- use of REFRESH PLUS greater than 4 times per day or within 6 hours prior to a study visit
- use of any topical ocular medication other than REFRESH PLUS
- use of Lacrisert™ (hydroxypropyl cellulose ophthalmic insert) or methylcellulose ocular inserts

The following procedures/treatments are prohibited during the study:

- insertion of punctal plugs
- punctal cautery in either eye
- use of contact lenses in either eye
- use of scleral lenses, or sealed compartment ocular frames
- LipiFlow or other lid-heating therapy, meibomian gland probing or therapeutic gland expression in either eye
- anterior segment surgery or trauma that could affect corneal sensitivity (eg, cataract surgery or any surgery involving a limbal or corneal incision) in either eye
- insertion or removal of glaucoma filtration shunts or devices

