4.5.3 Rescue Medications

In the event that rescue medication is required for worsening signs or symptoms of dry eye disease during the course of the study, patients will be provided an appropriate rescue regimen by the investigator/treating clinician, and be monitored through the end of the study.

5 Study Treatments

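### Section 8.9 takes a patient at unacceptable medical risk out of the study rather than off treatment, so scheduled safety follow-up stops even where no dose remains to be withheld

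*Protocol*

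**What the plan says.** Protocol Section 8.9 lets the investigator or the sponsor withdraw a patient and adds that, where feasible, "the decision to withdraw a patient from study treatment or the study should be discussed with Allergan". So it recognises two decisions. The criteria that follow have only one consequence: "Patients should be discontinued from the study if any of the following criteria are met". The first criterion is a new or exacerbated condition that the investigator believes "would put the patient at an unacceptable medical risk or compromises the patient's ability to participate in the study". The second is unwillingness or inability to comply. On what comes next, the section says: "Patients who are withdrawn early from the study during a study visit should have the exit procedures completed when possible".

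Other sections handle neighbouring situations differently:

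- Section 5.10, Stage 2: "If retreatment is not administered, the patient will continue to be observed for safety", with exit at Week 24/12R. A Stage 1 patient who is not retreated is likewise kept under observation.
- Section 4.5.3: a patient who needs rescue is to receive it "and be monitored through the end of the study".
- Section 4.5.1.1, pregnancy: "the patient will be exited from the study after appropriate safety follow-up".

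Some follow-up survives exit. Section 8.13 requires follow-up, as appropriate, of adverse events still ongoing at the exit visit. Section 8.14 requires serious adverse events (SAEs) to be reported for at least 12 weeks after the last dose, and every patient with an SAE to be followed with the outcome reported.

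In the SAP, Section 5.1.1.1.4 imputes no missing data. Table 5-18 closes the period for treatment-emergent adverse events (TEAEs) at the earlier of Week 24/12R and early termination.

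**The concern.** Stopping treatment protects a patient from a further dose. Leaving the study protects only from study procedures and restrictions. In a single-dose cohort there is no further dose after Day 1, so the medical-risk criterion, followed as written, removes scheduled observation from a patient who has already been dosed and about whom there is a safety worry.

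The SAP describes the study as a 24-week evaluation, with safety first among its aims. Protocol Section 1.1 says no human study of the product has been completed, and Stage 1 cohorts hold 3 to 8 patients. Under this rule a safety concern can itself shorten the record of the patient who raised it, and the missing observations cannot be recovered later.

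**Working it through.** **1. Who has no dose left.** Cohort sizes are in Protocol Section 4.1.

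- Plan's total: 3 (Cohort 1) + 3 × 4 (Cohorts 2, 6C, 6D) + 6 × 8 (Cohorts 3, 4, 5A, 5B, 6A, 6B) = 63. With up to 24 in Stage 2, 63 + 24 = 87. Both figures reproduce.
- Retreatment in Stage 1 is only for 6C and 6D (Section 5.10). Single-dose patients: 63 − 8 = 55, and 55/63 = 87%.
- Cohort 5B is not in the SAP cohort list (Section 5.1.1.1.2). Without its 8 patients: 47/55 = 85%.
- The other 8 in Stage 1 and up to 24 in Stage 2 have no dose left after Week 12. Before Week 12, exit does withhold a dose from them.

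These counts describe where exit withholds no drug. They do not estimate how many patients will exit.

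**2. What one exit costs in Cohorts 1 to 6B.** The documents give no withdrawal rate or timing, so exit time is varied as an assumption. Post-baseline timepoints come from the SAP: best-corrected visual acuity (BCVA) and hyperemia at Day 2 and Weeks 1, 2, 4, 8, 12 and 24 (7 visits; Tables 5-21, 5-22, 5-25); vital signs at Weeks 1, 8 and 24 (3 visits; Table 5-20). Assessments due at the exit visit are assumed done. Days lost = 168 − exit day.

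| Exit at | BCVA/hyperemia visits lost (of 7) | Vital-sign visits lost (of 3) | Days lost (of 168) |
|---|---|---|---|
| Week 1 (Day 7) | 5 | 2 | 161 |
| Week 2 (Day 14) | 4 | 2 | 154 |
| Week 4 (Day 28) | 3 | 2 | 140 |
| Week 8 (Day 56) | 2 | 1 | 112 |
| Week 12 (Day 84) | 1 | 1 | 84 |

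One patient is 1/8 = 12.5% of a cohort of 8 and 1/4 = 25% of a cohort of 4.

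**3. IOP and laboratory tests.** In Cohorts 1 to 6B their only post-baseline timepoint is Week 24 (Tables 5-19, 5-26). The window table for a baseline-and-Week-24 schedule is Table 6-9, which assigns every value from Treatment Day 2 onward to Week 24. If exit procedures yield a value on Day 14, it enters the Week 24 row although it was taken 168 − 14 = 154 days before the target. The patient then counts in N1 for that row. BCVA and vital signs behave differently: under Tables 6-2 and 6-5 the Week 24 window opens on Day 126 and Day 112, so an early leaver is absent from the row and N1 falls.

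**4. Adverse events.** New non-serious events are not collected once the patient has left. An SAE arising after exit is still reportable under Section 8.14 for the minimum period, but it falls after the TEAE tables close. For a single-dose patient that minimum ends at Week 12, leaving 24 − 12 = 12 weeks without a guaranteed reporting duty. For a retreated patient it runs to 12 + 12 = Week 24.

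**The case against.** The strongest reply is that the criterion is narrow and discretionary. It does not exit a patient for an adverse event as such. It needs an investigator's judgement of unacceptable risk, it says should rather than must, and the sponsor is to be consulted where feasible. With no dose left, an investigator could sensibly read the risk as coming from study procedures or restrictions, and then exit is right. The commonest safety situations already have rules that keep the patient in: no retreatment, rescue, and unscheduled visits with extra examinations (Section 8.6). This stands as a limit on how often the clause would bite. It does not remove the gap, because for this criterion the section offers study exit only and does not refer to Section 5.10.

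Second, the places where follow-up of discontinued patients might be specified (Section 8.4, most of the introduction to Section 8, and schedule Tables 3 and 4) are redacted or not shown. A mitigating rule there cannot be excluded. The eCRF is also unseen, and SAP Table 5-4 already lists study disposition and treatment-period disposition separately.

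A reader might also infer more than the documents support:

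- That safety follow-up stops altogether. It does not: exit procedures, follow-up of ongoing events, and SAE follow-up to outcome remain.
- That IOP and laboratory data are necessarily lost in Cohorts 1 to 6B. If exit procedures are done, a value exists. The problem is its Week 24 label.
- That 55 of 63 patients are affected. That is the number with no dose remaining.
- That dose escalation is compromised. The visible escalation steps in Section 3 use 2 weeks of monitoring, so later exits would not change them.

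**Conclusion.** The point holds as a low-cost improvement to the withdrawal rule. As written, the medical-risk criterion leads to study exit alone, and where no dose remains this ends scheduled observation of BCVA, hyperemia, vital signs and new non-serious events, as well as the TEAE tabulation period, without withholding any drug.

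The number affected is unknown and probably small. Per patient in Cohorts 1 to 6B, the loss for exits between Week 1 and Week 12 runs from 5 down to 1 of 7 BCVA and hyperemia visits. For most endpoints the gap would show in N1 and in the listing of premature discontinuations. For IOP and laboratory tests in those cohorts, N1 would not show it.

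This rests on three assumptions: that Section 8.9 is followed as worded, that no redacted text overrides it, and that Table 6-9 is applied to endpoints with the schedule it describes.

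**What to change.** In Section 8.9, split the first criterion. Make the unacceptable-medical-risk part stop any further study treatment, and keep dosed, consenting patients in the scheduled safety visits to Week 24/12R, as Sections 5.10 and 4.5.3 already do. State the exceptions: consent is withdrawn, the patient cannot attend or participate, or a study procedure is itself the risk, in which case only that procedure is omitted. Leave study exit as the consequence of inability to participate and of unwillingness or inability to comply. Record end of treatment separately from study exit if the eCRF does not already do so.

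The cost is one paragraph and perhaps one eCRF item. The downside is a few more visits for these patients, all of them already scheduled. Study restrictions need not stand in the way of their care, since Section 4.5.2 already provides: "The decision to administer a prohibited medication/treatment is done with the safety of the study participant as the primary consideration".
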